### 7.3. Study procedures

#### 7.3.1. Flowchart of treatment and examinations

NL48274.000.14

Phase I Study: Hespsecta vaccination in HPV+ lesions

**7.3.2. Schedule of events**

| Study Event   | Enrollment | Vaccination                  |                               |                              | Follow up                    |                                     |                                    |
|---|------------|------------------------------|-------------------------------|------------------------------|------------------------------|-------------------------------------|------------------------------------|
|   |            | First
Week 0  | Second
Week 3
(± 2days) | Third
Week 6
(± 2days) | First
Week 9
(± 2days) | Second
Week 17
(± 2
weeks) | Third
Week 26
(± 2
weeks) |
| Medical history / demographics                        | X          |                              |                               |                              |                              |                                     |                                    |
| In- / exclusion criteria                              | X          |                              |                               |                              |                              |                                     |                                    |
| Physical examination                                  | X          | X                            | X                             | X                            | X                            | X                       | X                                  |
| Concomitant medication                                | X          | X                            | X                             | X                            | X                            | X                                   | X                                  |
| Blood collection (Hematology, Chemistry)  | X          |                              | X                             | X                            | X                            |                                     | X                                  |
| Serum pregnancy test                      | X          |                              | X                 | X                |                              |                                     |                                    |
| Blood collection (immunology)             | X          |                              |                               | X                            | X                            |                                     | X                                  |
| Adverse events according to CTCAE criteria            |            | X                            | X                             | X                            | X                            | X                                   | X                                  |
| Hespsecta injection                                   |            | X                            | X                             | X                            |                              |                                     |                                    |
| Vital signs   | X          | X                | X                 | X                | X                            | X                       | X                                  |

: Baseline and first vaccination visit may be done on the same day;  In detail described in paragraph 7.8; : Female of child-bearing potential only; : Urinary pregnancy test also allowed; : HPV16 specific proliferation assay, IFN $\gamma$  ELISPOT and cytokine array; at baseline and early follow up visit also ex-vivo cytokine staining; : Before and after vaccination; : Shall not be performed if this visit is done by phone

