#### **4.4. Sample size calculation**

According to the clinical development paradigm for cancer vaccines as set by the Cancer Vaccine Clinical Trial Working Group (CVCTWG) [52] the current trial satisfies the criteria for being a proof-of-principle trial. The dose and schedule are investigated in proof of- principle trials, however, a definitive answer on the optimal setting for further trials should not be expected from a first-in-human study. For cancer vaccines, there may not be any linear association between dose, immunogenicity and clinical end points, therefore, the vaccine acute safety profile is not dose dependent. It is expected that the vaccine produces the desired biological effect across a broad-dose range. Primary end point used in this study is to determine biological activity i.e. T-cell immune response to the vaccine. Four different assays are used to evaluate the immunogenicity of Hespecta. These established complementary assays are conducted with blood samples taken at 4 time points (baseline and 3 follow-up time points after vaccine administration) , and are fully described in standard operating procedures (SOPs), including predefined criteria for positive and vaccine-induced response, and have been used and validated in a number of vaccine trials as published by our laboratory [17,32,33]. An immune response is identified if it was seen in at least 2 assays at 2 consecutive follow-up time points after the baseline assessment, in line with CVCTWG criteria. For proof-of-principle trials CVCTWG suggests a cohort size of at least 6 patients per dose [52]. As the CVCTWG already stated, the body of literature for optimizing the size of conventional phase 1 trials has little applicability to designing a proof-of-principle cohort trial because of the differences in the types of outcome measures and objectives. Here a cohort size of 6 patients per dose is used to determine safety and immunogenicity of Hespecta.

NL48274.000.14

Phase I Study: Hespsecta vaccination in HPV+ lesions

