## 7. METHODS

### 7.1. Main study parameter/endpoint

Primary objective is to determine the biological activity of Hespsecta that is able to induce HPV16 E6-specific T-cell immunity within a proposed dose escalation of 1, 5, 20 or 50 µg/peptide - conjugate in patients with HPV16+ tumors or premalignant lesions. Blood samples will be drawn and used in an array of complementary immunological assays (HPV16-specific proliferation assay, IFN $\gamma$ -ELISPOT, cytokine bead array and multiparameter flow cytometry analysis) to assess the biological activity of Hespsecta. These established assays are performed at 4 different time points (baseline and 3 time points after start of vaccination). Vaccine induced immunity in the different assays is defined if the response after vaccination is at least 3-fold higher than the pre-vaccination response. Biological activity is identified if it was seen in at least 2 assays at 2 consecutive follow-up time points after the baseline assessment, in line with CVCTWG criteria.

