### **7.9.3. Blood collection**

For hematology and biochemistry: 12.5 ml of venous blood (1 x 4 ml + 1 x 8.5 ml) will be obtained during the screening visit, before second and third vaccination (week 3 and 6, respectively) and at follow up (week 9 and week 26). For immunological assessment: 81 ml (9 x 9 ml) of venous blood will be obtained before vaccination (week 0), before third vaccination (week 6), at first follow up (week 9) and at third follow up (week 26). A total volume of 386.5 ml blood will be drawn during this trial.

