#### 7.9.5.3. HPV16 E6 and E7 peptide-specific IFN $\gamma$ -ELISPOT for CD4+ T-cells

The 4-day IFN $\gamma$ -ELISPOT for the detection of HPV16 E6 and E7 peptide-specific CD4+ T cells is our standard and validated assay. Spots are counted with a fully automated computer-assisted-video-imaging analysis system (BioSys 5000). Specific spots are calculated by subtracting the mean number of spots in quadruplicate wells + 2xSD of the medium only control from the mean number of spots in experimental wells. Antigen-specific T-cell frequencies are considered to be increased compared to non-responders when specific T-cell frequencies are  $\geq 1/10,000$ . T-cell frequencies are considered to be boosted by the vaccine when they were at least 3-fold higher than those prior to vaccination [10,55,56,57].

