#### 7.9.5.4. Ex-vivo HPV16 E6 and E7 peptide-specific responses

We have developed and validated a multiparameter flow cytometry assay. In this assay the HPV16-specific cytokines IFN $\gamma$  TNF $\alpha$ , and/or IL-2 producing CD4+ and/or CD8+ T cells can be simultaneously enumerated in combination with the activation markers CD154 and/or CD137. For this long overlapping HPV16 E6 and E7 peptides will be used to be able to detect both CD4 and CD8 T-cell responses in a HLA-independent setting as these long peptides harbor all potential CD4 and CD8 epitopes for every individual patient. Moreover, due to increased sensitivity in comparison to commonly applied intracellular cytokine staining (ICS) also low frequency antigen-specific T-cell responses can be detected directly ex vivo by using freshly isolated or cryopreserved PBMCs [58]. A positive response is defined as a frequency of activation marker expressing or cytokine producing T cells in the peptide stimulated condition which is twice above the medium only control. A vaccine-induced response is indicated by a 3-fold increase in frequency of antigen-specific T-cells (activation markers and/or cytokine production) compared to baseline values.

NL48274.000.14

Phase I Study: Hespecta vaccination in HPV+ lesions

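### The schedule gives flow cytometry one post-vaccination reading, while the endpoint text gives it three and requires responses at two consecutive follow-ups

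*Protocol*

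**What the plan says.** Section 7.1 lists the endpoint assays as HPV16-specific proliferation, IFNγ-ELISPOT, cytokine bead array and multiparameter flow cytometry. It then says: "These established assays are performed at 4 different time points (baseline and 3 time points after start of vaccination". It makes no exception for flow. The Synopsis says the same. Section 4.4 agrees: "Four different assays are used to evaluate the immunogenicity of Hespecta", and "These established complementary assays are conducted with blood samples taken at 4 time points".

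The responder rule in 7.1 is: "Biological activity is identified if it was seen in at least 2 assays at 2 consecutive follow-up time points after the baseline assessment". A response in an assay is a value at least 3 times the pre-vaccination value.

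Section 7.9.3 sets the post-baseline immunology draws: "before third vaccination (week 6), at first follow up (week 9) and at third follow up (week 26".

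Footnote 5 of the schedule of events (7.3.2) ties proliferation, ELISPOT and cytokine array to every immunology draw, but orders the fourth assay only "at baseline and early follow up visit also ex-vivo cytokine staining". That this is the flow assay follows by elimination, and from the title of 7.9.5.4, which describes the flow assay as the ex-vivo one.

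**The concern.** The footnote and the endpoint section order different data. A site or laboratory working from the schedule would produce one post-vaccination flow reading, whereas 7.1 promises three. The rule asks for responses at two consecutive follow-ups, and an assay read once after vaccination cannot show that by itself. So the contradiction affects who is a responder on the primary endpoint, and not merely the tidiness of the text. A later analysis plan cannot repair it, because it cannot supply readings that were never taken.

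The affected assay is also the one closest to the rationale. The Synopsis says a much stronger CD8+ response was needed for clinical efficacy, and 1.9 reports the conjugate's advantage in the CD8+ clone. Flow is the only assay described as separating CD8 from CD4 cells. The ELISPOT is presented as the test for CD4+ cells ("peptide-specific CD4+ T cells is our standard and validated assay"). Proliferation and the bead array are not described as separating the subsets.

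**Working it through.** **1. The plan's own figure.** 4 dose groups × 6 patients = 24, as stated. No power calculation applies; 9.1 plans descriptive statistics with 95% confidence intervals.

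**2. The two schedules side by side** (weeks from 7.9.3):

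| Assay | Under 7.1 | Under footnote 5 |
|---|---|---|
| Proliferation | 0, 6, 9, 26 | 0, 6, 9, 26 |
| ELISPOT | 0, 6, 9, 26 | 0, 6, 9, 26 |
| Bead array | 0, 6, 9, 26 | 0, 6, 9, 26 |
| Flow cytometry | 0, 6, 9, 26 | 0 and one early visit (6 or 9) |

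The consecutive follow-up pairs are weeks 6–9 and 9–26. With one flow reading, each pair contains at least one week without flow.

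**3. Two readings of the rule.** The text does not say which is meant.
- Reading A: the same two or more assays are positive at both consecutive time points.
- Reading B: any two or more assays are positive at each of them.

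**4. Reading A under footnote 5.** An assay counts only if it is positive at both weeks of a pair. Flow never can be, so every assay pair containing it drops out: C(4,2) = 6 pairs become C(3,2) = 3. One of those three, proliferation with bead array, rests on a single culture, because the bead array uses the proliferation supernatants (7.9.5.2).

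Count all positive/negative patterns: 3 assays × 3 weeks + 1 flow reading = 10 cells, and 2^10 = 1024 patterns. Flow changes responder status in 0 of 1024, whichever early week is used.

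**5. Reading B under footnote 5.** Flow matters only when, in its own week, it is positive with exactly one other assay (3 ways).
- Flow at week 9: at least one neighbouring week must have two or more of the other three assays positive. Each week does so in 4 of its 8 patterns, so 64 − 4 × 4 = 48 of the 64 combinations qualify. 3 × 48 = 144 of 1024.
- Flow at week 6: week 9 must have two or more positive (4 ways), and week 26 must not, or the patient already qualifies through weeks 9–26 (4 ways). 3 × 4 × 4 = 48 of 1024.

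**6. Flow at all three follow-ups, as in 7.1.** 12 cells, 2^12 = 4096 patterns. By enumeration flow decides status in 615 (reading A) or 1005 (reading B). These are counts of patterns, not probabilities.

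**7. A result common to both readings.** Take a patient positive only by flow and one other assay. At the week without flow, one assay is positive. One is less than two, so the patient is a non-responder under A and under B.

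**8. Size, under assumptions of my own.** Suppose assays and time points are independent with an equal chance of 0.3, 0.5 or 0.7 of a positive result. Under reading A the responder probability is 0.04, 0.26 or 0.65 with the footnote schedule, identical to having no flow assay. With flow at all three follow-ups it is 0.08, 0.41 or 0.83. Independence is doubtful, given the shared culture noted in step 4, so this shows direction only.

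One reclassified patient in a cohort of 6 moves the rate by 1/6 = 16.7 percentage points. For example, 4/6 (exact 95% CI 22.3–95.7%) becomes 3/6 (11.8–88.2%). Nothing in the protocol says how many patients, if any, would be affected.

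**The case against.** **The endpoint section may govern.** The Synopsis, 4.4 and 7.1 agree with each other, and 7.1 defines the endpoint. If it prevails, flow has three post-baseline readings and the design is sound. That is fair, and it is why the defect is a contradiction rather than a proven design fault. But nothing in the protocol says which text prevails, and the schedule is the part that sites execute.

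**A reader might infer that flow can never count toward the endpoint.** The documents do not support that. It needs both that footnote 5 governs and that the same assays must be positive twice. Under reading B one flow result can still decide status.

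**The footnote is loose.** It names no week. Section 9 calls week 26 late follow-up, so week 9 is the likely visit, with week 6 possible. If both were meant, flow could qualify at weeks 6–9 and would be decisive in 180 of 2048 patterns under reading A. The wording is singular, however, and two readings would still contradict 7.1.

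**A reader might also infer that the trial cannot answer its CD8 question.** That goes too far. The primary objective is HPV16 E6-specific T-cell immunity, not CD8 immunity. Flow counts CD4+ and/or CD8+ cells, so a flow positive need not be a CD8 response, and even the full schedule would not make the composite CD8-specific. Section 7.9.5.4 defines a vaccine-induced response as a 3-fold rise over baseline, which one post-vaccination sample can show, and 9.1 allows it to be described. CD8 responders may also register in the proliferation and bead-array assays.

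**The stakes are descriptive.** No test rests on the rule, and the IDMC charter (14.2.2) bases dose escalation on safety data only. This stands. The consequence is confined to responder classification and the reported rates.

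**Conclusion.** The contradiction is real and nothing in the protocol resolves it: one post-baseline flow reading in footnote 5 against three in the Synopsis, 4.4 and 7.1. If the footnote is followed, flow cannot be positive at two consecutive follow-ups. Its contribution is then nil under reading A and limited to one of the two time points under reading B. The non-responder result in step 7 depends only on the footnote being followed, not on the choice of reading. The fall from 6 usable pairs to 3 depends on the footnote and on reading A together. The loss to the CD8 question is that the only subset-resolving assay has a restricted or absent role in the composite, not that CD8 results are unobtainable. The 16.7-point shift is illustrative and is no estimate of bias.

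**What to change.** Preferred: correct footnote 5 so that flow is run at weeks 0, 6, 9 and 26, as 7.1 states. The 81 ml immunology sample is already drawn at all four time points, and 7.9.5.4 permits the assay to be done "by using freshly isolated or cryopreserved PBMCs". The cost is at most 3 − 1 = 2 extra runs per patient, 2 × 24 = 48 in total, with no extra visit, blood or patients.

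Otherwise: amend the Synopsis, 4.4 and 7.1 to say that flow has one post-baseline reading, name its week, and state either how that reading counts toward the endpoint or that flow is reported separately. This costs wording only.

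In both cases, add a sentence to the responder rule saying whether the same two assays must be positive at both consecutive time points.

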## 7.4. Schedule

### 7.4.1. Screening and confirmation of eligibility (Week -2 to week 0)

No screening assessments will be made or any procedure performed before the patient has given written informed consent. If possible screening and first vaccination visit will be done on the same day. The following assessments will be made and procedures will be performed during the screening period (up to 2 weeks before the first vaccination):

- Medical history
- Collection of patient demographic information
- Evaluation of inclusion/exclusion criteria
- Standard physical examination
- Documentation of concomitant medications
- Documentation of baseline status of HPV16+ tumor or premalignant lesion (date of diagnosis, prior therapy, extent of lesions)
- Collection of blood samples for safety parameters (Chemistry and hematology, see paragraph 7.8)
- Collection of blood samples for immunology
- Serum pregnancy test (female of child-bearing potential only)
- Vital signs (heart rate, respiratory rate, body temperature and blood pressure)

### 7.4.2. Vaccination 1 (Week 0)

Prior to vaccination:

- Inspect the intended vaccination site for any skin abnormalities. Only continue vaccination when the skin is intact
- Vital signs (heart rate, respiratory rate, body temperature and blood pressure)

Vaccination:

- Inject the vaccine i.d. in either one of the thighs or of the upper arms. Injection may only be done by qualified study staff under medical supervision.

1 hour after each vaccination:

- Vital signs (heart rate, respiratory rate, body temperature and blood pressure)
- Examination of the inoculation site
- Registration of AE (with special emphasis on the vaccination sites)

### 7.4.3. Vaccination 2 (Week 3 ± 2days) and vaccination 3 (Week 6 ± 2days)

Before second and third vaccination:

NL48274.000.14

Phase I Study: Hespecta vaccination in HPV+ lesions

- Inspect the intended vaccination site for any skin abnormalities
- Standard physical examination
- Vital signs (heart rate, respiratory rate, body temperature and blood pressure)
- Collection of blood samples for safety parameters (Chemistry and hematology, see paragraph 7.8)
- Collection of blood samples for immunology (only before third vaccination)
- Documentation of concomitant medications
- Urine pregnancy testing (female of child-bearing potential only)
- Documentation of AE (with special emphasis on the vaccination site)
- Inspection and measure of previous inoculation sites

Vaccination:

- Inject the vaccine i.d., in either one of the thighs or of the upper arms. Injection may only be done by qualified study staff under medical supervision.

1 hour after each vaccination:

- Vital signs (heart rate, respiratory rate, body temperature and blood pressure)
- Examination of the inoculation site, and also of previous inoculation sites
- Registration of AE (with special emphasis on the vaccination sites)

#### **7.4.4. Follow up for immunological and safety assessments (Week 9 ± 2 days)**

Patients will return to the clinic 3 weeks ± 2 days after the last vaccination for assessment of the immunological parameters.

- Standard physical examination
- Documentation of concomitant medications
- Collection of blood samples for safety parameters (Chemistry and hematology, see paragraph 7.8)
- Collection of blood samples for immunology
- Documentation of AE (with special emphasis on the vaccination sites)
- Inspection and measure of previous inoculation sites

#### **7.4.5. Follow up for immunological and safety assessments (Week 17 ± 1 week), (Week 26 ± 1 week)**

- Patients will return to the clinic 11 weeks ± 1 week) and 20 weeks ± 1 week after the last vaccination for assessment of the immunological and safety parameters. These visits are combined with regular follow up visits. If during the first follow-up visit (week 9) no abnormalities are found, it is to be expected that also at the second monitoring visit no abnormalities are found. Therefore if no abnormalities are found during the first monitoring

visit, the second monitoring visit may take place by telephone (week 17). Standard physical examination

- Documentation of concomitant medications
- Collection of blood samples for safety parameters (Chemistry and hematology, see paragraph 7.8), only week 26 ± 1 week
- Collection of blood samples for immunology, only week 26 ± 1 week
- Documentation of AE (with special emphasis on the vaccination sites)
- Inspection and measure of previous inoculation sites

#### **7.5. Withdrawal of individual subjects**

Subjects can leave the study at any time for any reason if they wish to do so without any consequences and without any explanation. Such patients will be considered as withdrawals. The reason(s) for withdrawal must be obtained and documented, e.g. patient refusal, with medical reasons to be specified. The investigator can decide to withdraw a subject from the study for urgent medical reasons. After enrolment of a patient, the investigator may start treatment concomitant to that specified in the protocol if this is considered to be in the patient's best interest, but the reasons for doing so should be recorded. If such concomitant treatment does not conflict with the in- and exclusion criteria, the patient remains on study and will keep on receiving treatment according to the protocol.

#### **7.6. Replacement of individual subjects after withdrawal**

Patients who withdraw from the study due to unacceptable toxicity of the study drugs will not be replaced. In order for patients to be eligible for immunological evaluations they have to fulfil all of the below listed criteria:

- Patients should have received at least two doses of Hespecta
- For immunological assessment the patients should have given blood samples for immunological assays (i.e. at baseline (week 0), and at least two of the following time points: before vaccination 3 (week 6) at first follow up, 3 weeks after the third vaccination (week 9), or at late follow up (week 26). Blood samples should have sufficient cell numbers of PBMCs ( $\geq 40 \times 10^6$ ). Patients of whom PBMC counts are not sufficient will be replaced to be able to determine the objectives of this study.

